5.2 STUDY POPULATION

5.2.1 Approximate Number of Subjects: 55

5.2.2 INCLUSION CRITERIA

- 1. Patients requiring restorative or surgical dental treatment on two or more occasions on opposite sides of the mouth; either both maxillary or both mandibular quadrant/sextant involving comparable teeth/areas
- 2. Patients able to undergo dental treatment in the dental clinic without general anesthesia, sedation, or anxiolysis
- 3. Patients 4-17 years of age
- 4. Patients classified as ASA I or ASA II
- 5. Patients of parents who can read, write and give consent in English

5.2.3 EXCLUSION CRITERIA

- 1. Patients with allergy to local anesthetic
- 2. Patients who are pregnant or nursing
- 3. Patients with cardiac concerns or contraindications to epinephrine
- 4. Patients unable to undergo dental treatment in the clinic for behavior or medical reasons
- 5. Patients requiring anxiolysis, sedation, or general anesthesia
- 6. Patients unable to keep dental appointments or return for dental appointments
- 7. Patients who do not meet inclusion criteria
- 8. Patients who experience a missed block (IANB) during injection

5.3 RECRUITMENT

Study participants will be screened by a treating dentist from a GMC dental clinic at time of comprehensive oral exam or periodic oral exam. Patients may be added to the study by the treating dentist based on the inclusion criteria. Study participants will be recruited from the outpatient Foss clinic of Geisinger Medical Center in Danville, PA and from the outpatient Milton clinic of Geisinger Medical Center in Milton, PA.

IRB NUMBER: 2019-0408 IRB Approved: 12/12/2019

Recruitment of study participants will be done by the treating pediatric dental resident or attending pediatric dentist at the time of exam. Patients will be recruited from the outpatient Foss clinic in Danville, PA and the outpatient Milton clinic in Milton, PA at Geisinger Medical Center.

5.4 STUDY DURATION

- 5.4.1 Approximate Duration of Subject Participation: 2 or more dental visits, with each visit lasting between 30-90 minutes
- 5.4.2 Approximate Duration of Study: 12 months

5.5 STATISTICS

5.5.1 Statistical Analysis Plan

Data will be analyzed using t-tests to examine treatment differences. Given patients will be treated with both methods, they will act as their own controls and paired t-tests will be utilized. If covariates are identified (e.g., patients' baseline pain perception), Repeated measure ANOVAs will be utilized with patients as within-subject variable and the patient experience as the outcome.

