This project's primary aim is to evaluate pain perception in buffered vs non-buffered local anesthetic administration in children undergoing routine dental treatment. The secondary aim is to evaluate if the buffered solution results in a faster onset of local anesthesia compared to conventional solution. Through a well-designed study, we hope to contribute to the profession's understanding of advanced local anesthesia techniques in children.

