4. HYPOTHESIS AND SPECIFIC AIMS

4.1 HYPOTHESIS:

- 4.1.1 Null Hypothesis: There will be no significant difference between buffered local anesthesia vs conventional anesthesia in pain reduction.
- 4.1.2 Null Hypothesis: There will be no significant reduction in time between buffered local anesthesia vs conventional anesthesia achieving soft tissue anesthesia.
- 4.1.3 Hypothesis: There will be a statistically significant reduction in pain on intraoral administration of buffered 2% lidocaine with 1:100,000 epinephrine compared to non-buffered 2% lidocaine w/1:100,000 epinephrine in children.
- 4.1.4 Hypothesis: Buffered 2% lidocaine with 1:100,000 epinephrine will have a statically significant faster onset of soft tissue anesthesia compared to non-buffered 2% lidocaine w/1:100,000 epinephrine in children

4.2 SPECIFIC AIM 1:

To determine if buffering 2% lidocaine with 1:100,000 epinephrine reduces discomfort experienced on injection compared to non-buffered solution in children with a split mouth design

4.3 SPECIFIC AIM 2:

To compare infiltration vs inferior alveolar nerve block (IANB) in experience of pain reduction with buffered 2% lidocaine with 1:100,000 epinephrine on injection in children among different groups; patients will either receive two or more infiltrations or two or more IANBs.

4.4 SPECIFIC AIM 3:

To determine if buffering 2% lidocaine with 1:100,000 epinephrine reduces onset time of local anesthesia compared to non-buffered solution in children

4.5 SPECIFIC AIM 4:

[figure not shown]
To compare onset time of local anesthetic via infiltration versus IANB using buffered 2% lidocaine with 1:100,000 epinephrine in children

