Topical 20% benzocaine (Ultracare Oral Anesthetic Gel, Ultradent, South Jordan, Utah will be used on the intraoral tissue at site of injection for 5 minutes, and then the tissue will be injected. Patients will be informed when the tissue is pierced and again when the local anesthesia is being administered. Participants receiving an IANB will be injected with 0.85mL (50% volume of a 1.7mL carpule) of 2% lidocaine with 1:100,000 epinephrine approximately. Patients receiving a buccal infiltration in the maxilla will receive 0.425mL (25% volume of a 1.7mL carpule) of solution over 15 seconds. The operator will aspirate prior to administration of local anesthetic solution in all cases; a positive aspiration will require redirection of the needle or repositioning before injection. Patients will be asked to rate their pain related to administration of solution (the second prompt) once the injection is finished. Patients will be observed during injection and assessed by the operator using the Faces, Legs, Arms, Crying Consolability (FLACC) scale. Immediately after local anesthesia, patients will be asked to rate the pain of injection of solution using the Wong-Baker FACES Pain Scale. These scales were selected because they are approved for use by the AAPD for children over the age of 3 and have been used successfully in previous studies investigating pain perception in child subjects.^{7,14}

After administration of local anesthetic solution, the onset time of soft tissue anesthesia will be measured by using a periodontal probe in the sulcus of the anesthetized tooth or a single tooth in the anesthetized quadrant. This probing will be initiated 15 seconds after initial injection of anesthetic solution and will be repeated at 15 second intervals until local anesthesia is achieved. After each probing attempt, patients will be asked if they felt a "pinch". Once the patient answers "no," the time of onset, in number of seconds to achieve anesthesia from injection to a "no" answer, will be recorded.

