In the event of a missed block, the patient will be excluded from the study. The second attempt for local anesthesia will be made with the effort to achieve profound local anesthesia, and the technique and type of local anesthesia will not be limited to the techniques or anesthetic solutions described in this study. Local anesthesia techniques and solutions used in the event of a missed block will be within the scope of practice for a pediatric dental patient, however, this event will be considered a potential confounding variable in our research study.

A second protected Excel spreadsheet will be used to record patient's scores for the Wong-Baker FACES Pain Scale, the FLACC scale and the time of onset of local anesthesia. This spreadsheet will also include the patient's name, MRN number, the side of the mouth that was treated, the location of the injection, the injection technique, and the date of each visit. This spreadsheet will be available to the operator in order to record the clinical outcomes related to each encounter; it will not affect the double-blind nature

GEISINGE IRB NUMBER: 2019-0408 IRB Approved: 12/12/2019

of this study, as the operator will not know which local anesthetic preparation was used during each encounter.

After the first day of treatment, a "wash out" period of at least 1 week will be required before the patient can return for treatment on the other side of the mouth, and the administration of the alternate type of local anesthetic solution. Wash out periods have been used in many similar studies to minimize bias.^{1,7,11}

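### The primary pain hypothesis is measured on two unranked scales; if a significant result on either counts, the false-positive rate is about 7% to just under 10% rather than 5%

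*Combined protocol and SAP*

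**What the plan says.** Section 3 states that the project's "primary aim is to evaluate pain perception in buffered vs non-buffered local anesthetic administration in children" and ranks onset of anesthesia as the secondary aim. Hypothesis 4.1.3 reads: "There will be a statistically significant reduction in pain on intraoral administration of buffered 2% lidocaine", compared with the non-buffered solution. Neither place names an instrument.

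Section 5.1 takes two pain measurements for the same injection. From the child: "Immediately after local anesthesia, patients will be asked to rate the pain of injection of solution using the Wong-Baker FACES Pain Scale". From the operator: "Patients will be observed during injection and assessed by the operator using the Faces, Legs, Arms, Crying Consolability (FLACC) scale". A results spreadsheet will then "record patient's scores for the Wong-Baker FACES Pain Scale, the FLACC scale and the time of onset of local anesthesia", with no ranking among the three.

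The analysis plan in 5.5.1 is three sentences long. The first is "Data will be analyzed using t-tests to examine treatment differences". The second says that because patients receive both solutions "they will act as their own controls and paired t-tests will be utilized". The third applies only if covariates are identified; it moves to repeated-measures ANOVA and takes the patient's experience as the outcome, again without naming a scale. Section 5.5.2 powers the study on one standardized effect, d = 0.50, and does not say which scale it belongs to.

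**The concern.** One hypothesis is served by two measurements, and the plan does not say how they combine into one conclusion. A t-test on each scale is the natural reading of 5.5.1, and nothing there prevents a significant result on whichever scale succeeds from being reported as confirming 4.1.3. That would give the primary claim two chances at the nominal level. A primary scale picked after the solution codes are known could not repair this, because the choice could follow the result.

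There is also an interpretive gap that does not depend on any error rate. If FACES shows a difference and FLACC does not, or the reverse, both results can be reported, but the plan gives no basis for saying whether the primary aim was met.

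**Working it through.** **Inputs.** From 5.5.2: d = 0.50, 90% power, 44 evaluable pairs, 55 enrolled, 20% attrition. Not stated anywhere: the significance level, its sidedness, and the correlation r between the FACES and FLACC paired differences. I assume two-sided 5% and show r from 0 to 0.9.

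**1. The plan's own figure.** For a paired t-test with n = 44, df = 43 and noncentrality 0.5 × √44 = 3.317, the two-sided 5% critical value is 2.017 and the power is 0.900. The smallest n that reaches 90% is 44, and 44 / 0.80 = 55. The stated sample size is reproduced. A one-sided 5% test would need only 36 pairs and would have 94.7% power at 44, so the stated size fits two-sided 5% (or, equivalently for this purpose, one-sided 2.5%). That supports the assumed level but does not replace a statement of it.

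**2. False-positive rate if either scale suffices.** With no true effect on either scale,

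P(at least one significant) = 0.05 + 0.05 − P(both significant).

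At r = 0, P(both) = 0.05 × 0.05 = 0.0025, so the rate is 0.10 − 0.0025 = 0.0975. For r > 0, P(both) comes from the bivariate normal distribution with limits ±1.96. Counting only results that favour buffering, the formula is 0.025 + 0.025 − P(both favourable); at r = 0 this is 0.05 − 0.000625 = 0.0494.

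| r | Either scale, any direction | Either scale, favouring buffering |
|---|---|---|
| 0 | 9.75% | 4.9% |
| 0.3 | 9.5% | 4.8% |
| 0.5 | 9.1% | 4.5% |
| 0.7 | 8.3% | 4.2% |
| 0.8 | 7.8% | 3.9% |
| 0.9 | 7.0% | 3.5% |
| One scale only | 5.0% | 2.5% |

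Simulated paired t-tests with n = 44 agree with the first column to within simulation error.

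**3. Other decision rules.** If both scales had to be significant, the rate would be P(both) = 0.10 minus the first column: 0.25% at r = 0 and 3.0% at r = 0.9, so there would be no inflation. If FACES alone decided, it would be 5%.

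**4. What each remedy does to power.** With one scale primary at two-sided 5%, 44 pairs keep 90.0% power. With both scales kept and 5% split equally (2.5% each), power at 44 pairs falls to 83.6% per scale; 90% would need 53 pairs, and 53 / 0.80 = 66.25, so 67 enrolled.

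**The case against.** The strongest reply is that the plan never says either scale suffices. Section 5.5.1 lists no outcomes, so FACES as the sole decider, or a requirement that both be significant, fits the text equally well, and neither inflates error. This stands, and it makes the inflation conditional. It does not remove the omission, because no such rule is written.

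A second reply is that the documents already lean towards self-report. Section 3 speaks of perception, Aim 1 of discomfort as experienced, and the conditional ANOVA sentence of the patient's experience; the only baseline pain rating described is FACES. This is fair, and it is a good reason to choose FACES. But none of these places designates a primary outcome, the ANOVA wording does not govern the default paired t-tests, and 5.1 presents both scales as measures of pain perception.

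Three stronger readings are tempting, and the documents do not support them:

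- **That the error rate is nearly doubled.** That is the figure for uncorrelated scales. Both scales rate the same injection in the same child, so positive correlation is to be expected, and at r = 0.9 the factor is 1.4 (7.0 / 5.0). The documents give no correlation.
- **That onset makes a third chance,** at about 14% if all three tests were independent (1 − 0.95³ = 0.143). Section 3 already ranks onset as secondary, and 4.1.2 and 4.1.4 give it its own hypotheses. A test of onset cannot produce a false claim about pain.
- **That FLACC is biased because the person injecting scores it.** Section 5.1 blinds the operator to the solution, and the documents show no route by which expectation would favour one arm.

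**Conclusion.** The concern holds as a conditional one. The documents establish that one primary pain hypothesis rests on two unranked scales, with no primary scale and no rule for multiplicity or disagreement. They do not establish that the investigators will count success on either scale.

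If they did, with two-sided 5% tests, the false-positive rate would be 7.0% to 9.75% over the range of r shown. For the directional claim actually made in 4.1.3 it would be 3.5% to 4.9% against 2.5%, which remains below 5% in absolute terms. The size rests on three assumptions: the either-scale reading, the inferred significance level, and the unknown correlation. The missing decision rule for discordant scales rests on none of them. This should be corrected, but it does not undermine the design or the sample size.

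**What to change.** Before unblinding, amend 5.5.1 to state that:

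- the single primary outcome is the child's post-injection FACES rating, compared between solutions as a within-child paired difference at two-sided 5%;
- FLACC is supportive, reported with its estimate and interval, and cannot by itself meet the primary aim;
- onset time remains the secondary aim. Whether to test it only after a significant FACES result is a design preference, and this point does not require it.

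In 5.5.2, state that d = 0.50 and 90% power refer to the FACES paired difference. The documents do not say which scale the cited effect came from, so this should be confirmed or labelled as a planning assumption.

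The cost is wording only: 44 evaluable and 55 enrolled are unchanged. The downside is that a result seen on FLACC alone could no longer be claimed as meeting the primary aim. Keeping both scales as co-equal with a split significance level is also valid, but it costs either power (83.6% per scale at 44 pairs) or 12 more enrolled children (67 − 55).

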5. STUDY DESIGN

5.1 DESCRIPTION

This study has been designed as a longitudinal, double blind, crossover study. Specifically, a split mouth design will be implemented to investigate if there is a significant difference in pain perception between administering buffered local anesthesia versus conventional local anesthesia in a pediatric patient. We will also investigate time of onset of local anesthesia and compare buffered to non-buffered solutions. Patients will be treated by a single pediatric dental resident while being overseen by a board-certified attending pediatric dentist at Geisinger Medical Center (GMC). This study will be implemented upon receiving Institutional Review Board (IRB) approval.

The population of interest includes healthy children aged 4-17yo. Children selected for this study will be assessed using the American Society of Anesthesiologists (ASA) physical status classification system. In an effort to control for confounding variables, only healthy children classified as ASA I or ASA II will be included in this study. Children selected for this study will have been determined to require treatment on two or more occasions on opposite sides of the mouth. If a patient has multiple issues on each side of the mouth, the patient may be asked to participate in the study procedures for a second time. This could result in seeing the patient for 4 separate visits. Patients will not be excluded if they develop localized infection requiring treatment without systemic antibiotics, however, they will only remain in the study if both sides requiring treatment are either free of infection or if both sides have a localized pain or infection requiring treatment without systemic antibiotics. Patients must have no allergy to lidocaine or

history of adverse reactions to epinephrine, no history of hyperthyroidism, and no significant cardiovascular disease per recommendations for administration of local anesthetic according to the American Academy of Pediatric Dentistry (AAPD).¹² Buffered lidocaine has been approved for use in patients for medical and dental procedures. There is no additional cost to the patient for receiving buffered versus non-buffered solution.

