On the day of the procedure, the side of the mouth that is treated first will be based on the patient's chief complaint. If the patient does not have a chief complaint, the side of the mouth that is treated first will be the side of the mouth with more significant dental caries. The attending pediatric dentist will flip a coin to determine if the patient will receive the buffered or conventional local anesthetic solution during the first visit, with the "heads" side being assigned to the buffered solution, and the "tails" side assigned to the non-buffered solution. At the patient's second visit, the alternative local anesthetic solution will be used, and the other side of the mouth will be treated.

IRB NUMBER: 2019-0408 IRB Approved: 12/12/2019

[figure not shown]
The attending pediatric dentist will have access to a protected Excel spreadsheet containing information related to each patient including: patient name, medical record number (MRN), the patient's number assignment (as discussed above), date of the first and second visit, which local anesthetic solution was administered at each visit, the local anesthesia technique used (infiltration vs IANB), which arch (maxilla vs mandible) was treated, and which side of the mouth was treated. This document will be locked and the operator will not have access to this spreadsheet in order to preserve the double-blind nature of this study.

Vasoconstrictors, like epinephrine, become unstable with an increase in pH⁹. Local anesthetic solutions with a vasoconstrictor are traditionally prepared as an acidic solution to extend shelf life⁹. Buffering our local anesthesia containing epinephrine will reduce the stability of solution from approximately 8-12 months to a shelf life of only seven days¹³. Although the solution has been said to be stable for a week, to ensure stability of the solution, and control for confounding variables, the buffered solutions will be mixed immediately before administering the solution. Other study designs have used this approach to mix the solution immediately before administration^{1,9}.

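### Prespecify a visit term in the primary paired analysis: a low-cost improvement, not the correction of an error

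*Combined protocol and SAP*

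**What the plan says.** Section 5.5.1 plans t-tests for treatment differences. Because each child receives both solutions, "they will act as their own controls and paired t-tests will be utilized". Repeated-measures ANOVA replaces this "If covariates are identified". Baseline pain perception is the only example given, and visit is not named.

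Section 5.1 sets the order of events:

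- Side: "the side of the mouth that is treated first will be based on the patient's chief complaint"; without a chief complaint, "the side of the mouth that is treated first will be the side of the mouth with more significant dental caries".
- Solution: the attending dentist "will flip a coin to determine if the patient will receive the buffered or conventional local anesthetic solution" at the first visit. No blocking is described.
- Second visit: "the alternative local anesthetic solution will be used, and the other side of the mouth will be treated".
- Records: the attending's spreadsheet holds the "date of the first and second visit, which local anesthetic solution was administered at each visit".
- Repeat participation: for a child with several problems on each side, "the patient may be asked to participate in the study procedures for a second time", which could mean four visits.

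Section 5.5.2 gives 90% power for a standardised effect of 0.50, 44 evaluable patients, and 55 enrolled to allow for 20% attrition.

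**The concern.** Visit 1 and visit 2 are not exchangeable. Visit 1 treats the side that is the chief complaint or has the worse caries, and visit 2 always follows an earlier study injection. Either could change how a child rates or shows pain.

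Other rules limit this difference without removing it. The inclusion criteria in 5.2.2 ask for comparable teeth in the same arch. Section 5.1 requires the same infection status on both sides and at least one week between visits. Comparable teeth can still differ in caries, and a week does not remove the memory of an injection.

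The solution given at visit 1 is randomised, so a visit difference does not favour either solution on average. In a paired t-test without a visit term, however, the difference goes into the error. If the coin happens to send more children to one order, part of it is also read as a solution effect. Adjustment is possible under the ANOVA sentence, but 5.5.1 has no rule for when that sentence applies, so the choice could be made after the data are seen.

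**Working it through.** **1. The plan's own figure.** Inputs from 5.5.2: effect 0.50, read as mean paired difference divided by its SD, and n = 44. The significance level is not stated; two-sided 5% is assumed. The noncentral t has 43 df and noncentrality 0.50 × √44 = 3.317, which gives power 90.0%. Enrolment is 44/0.80 = 55. Both figures reproduce.

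**2. Model.** Write the buffered-minus-conventional difference as τ + s·d + e. Here s = +1 if buffered came first and −1 if it came second, d is the visit-1 minus visit-2 mean, and SD(e) = 1. The documents give no d, so a range is shown.

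- Paired t-test: variance per child over coin flips is 1 + d², with 43 df.
- With a visit term: SE = ½√(1/n1 + 1/n2), with 42 df, averaged over Binomial(44, 0.5) splits. Chance imbalance inflates the variance by 1.0245 on average.

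| d (SD of paired difference) | Paired t-test | With visit term |
|---|---|---|
| 0 | 90.0% | 89.3% |
| 0.10 | 89.7% | 89.3% |
| 0.16 | 89.3% | 89.3% |
| 0.25 | 88.2% | 89.3% |
| 0.50 | 82.6% | 89.3% |

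Break-even is d = 0.161. The gain at 0.50 is 89.26 − 82.63 = 6.6 points. If the SD behind the planning effect already contains visit variation, the planned test keeps its 90%, and adjustment gives 89.6%, 91.0% and 94.7% at d = 0.10, 0.25 and 0.50. Break-even is again 0.16.

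**3. Shift in one trial.** The unadjusted estimate moves by d × (n1 − n2)/44. The mean of |n1 − n2|/44 is 0.12, so the average shift is 0.03 SD at d = 0.25 and 0.06 SD at d = 0.5. A split of 27/17 or worse has probability 17%. At 27/17 and d = 0.5 the shift is 0.5 × 10/44 = 0.11 SD.

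**4. Type I error of the unadjusted test (simulation).** At d = 0.5 it is about 2.8% given a 22/22 split and about 7.7% given 27/17. Over all splits it is about 5%.

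**5. Adding per-visit baseline FACES (simulation on the difference scale, d = 0).** If the baseline difference is unrelated to the outcome difference, power is about 88.5% under coin flips, a cost of about 1.5 points. At 22/22 the cost is 0.6 to 0.8 points. Break-even rises to about 0.23 SD. The loss is recovered once the two differences correlate at about 0.2 or more.

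**6. Repeat participants.** The documents do not say how many children will repeat. Assume 11 of 44 add a second pair and all 55 pairs are treated as independent. With correlation ρ between a child's two differences, the variance of the mean is understated by a factor of about 1 + 2 × 11ρ/55: 1.12 at ρ = 0.3 and 1.20 at ρ = 0.5. Type I error is then about 6.5% and 7.3%.

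**The case against.** The strongest reply is that nothing here is wrong. Solution order is randomised, so side priority and prior injection experience balance in expectation. The paired t-test is unbiased, and no figure in 5.5.2 fails. That stands in full.

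A reader might go further and infer that the test is biased, that its type I error is inflated, or that the trial is underpowered. The documents support none of these. The shift arises only within an unevenly split trial. The excess error at 27/17 is offset by a conservative test near balance. A power shortfall would need a visit effect that the documents do not quantify.

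Second, the gain rests on an assumed quantity. The eligibility rules and washout push d down, and the 6.6-point gain needs a visit effect as large as the treatment effect the trial is powered for. This also stands, and it limits the claim to small cost against possible gain.

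Third, 5.5.1 already allows covariates, and baseline FACES could absorb a side difference that shows as pain before treatment. This stands in part. The plan permits adjustment but does not commit to it. The baseline covariate also has a cost of its own, so the 0.7-point figure must not be quoted for a model that includes it.

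Fourth, repeat pairs are a different issue. That is right, and the point is kept separate below.

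**Conclusion.** A cheap improvement is available; there is no error to correct. The planned test is valid over coin flips and the sample size is sound. A prespecified visit term costs at most about 0.7 points of power and pays back if the visit effect exceeds about 0.16 SD of the paired difference. It also removes the shift that comes with an uneven split and settles the model before data are seen. These figures assume 44 evaluable children, a two-sided 5% level and an effect of 0.50. Whether the visit effect passes the threshold cannot be learned from the documents.

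The repeat-participation gap is independent of any visit effect. Its size depends on the assumed 11 repeaters and the assumed correlations. If the two differences are uncorrelated, type I error stays near 5%.

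**What to change.** In 5.5.1, replace the paired t-test and the open-ended covariate trigger with one primary model for the pain score at injection: solution and visit (1 or 2) as fixed effects, patient as a random effect. An equivalent is a two-sample t-test that compares visit-1-minus-visit-2 differences between the two orders, with the mean difference halved. The data are already recorded and no patients or visits are added. The cost is one degree of freedom and about 0.7 points of power if there is no visit effect.

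Per-visit baseline FACES may be added as a prespecified covariate. The plan should then state the cost as about 1.5 points under coin flips (0.6 to 0.8 at 22/22), with break-even about 0.23 SD, if baseline is unrelated to outcome. Section 5.1 should also say that the baseline is taken at both visits, because the main effect of a single baseline per child cancels from the within-child contrast.

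Optionally, for children not yet allocated, use a permuted-block list for solution order. At 22/22 the visit-only model has 89.97% power, so its cost falls to about 0.03 points. The rule for which side goes first need not change.

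Separately, state that the primary analysis uses each child's first pair. The sample size counts patients, so planned power is unaffected. Second pairs can enter a sensitivity analysis with a patient-by-solution random effect.
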